ICH	The International Council for Harmonisation of Technical Requirements for Pharmaceuticals for Human Use
IND	Investigational New Drug Application
IRB	institutional review board
ISBT	International Society of Blood Transfusion
IVIG	intravenous immune globulin
JAMA	Journal of the American Medical Association
LIP	Licensed Individual Practitioner
MMWR	Morbidity and Mortality Weekly Report
MN	microneutralization
NAT	nucleic acid testing
OTC	over the counter
PCCP	Penn COVID-19 Convalescent Plasma
PCR	polymerase chain reaction
PK	pharmacokinetic
RSV	respiratory syncytial virus
SAE	serious adverse event
SARS	severe acute respiratory syndrome
TRALI	transfusion-related acute lung injury
VIG	vaccinia immune globulin

1 STUDY SUMMARY

1.1 Synopsis

Title: An Open-Label, Controlled, Phase 1, Safety and Exploratory Efficacy Study of Convalescent Plasma for Severely Ill, Hospitalized Participants with COVID-19 Pneumonia Caused by SARS-CoV-2.

Short Title: COVID-19 Convalescent Plasma for Hospitalized Population

Study Description: This open-label, controlled, phase 1 trial will assess the safety and efficacy of convalescent plasma in severely ill, hospitalized participants with pneumonia due to COVID-19. This study will enroll adults 18 years old and older, including pregnant women.

A total of 80 eligible participants will be randomized to receive either 2 units of convalescent plasma collected from ABO-compatible donors who have recovered from COVID-19 and standard of care (treatment arm) or standard of care alone (control arm). Participants in the treatment arm will receive 2 units of convalescent plasma on Study Day 1 in addition to standard of care.

Participants will be assessed on study Day 1 (pre-dose), 30 minutes after each unit of plasma, on all Study Days while hospitalized, and Study Days 15, 22, 29, and 60. All participants will undergo a series of safety and efficacy, assessments. Blood samples will be collected on Days 1 (prior to plasma administration), 3, 8, 15, 29, and 60. Oropharyngeal or endotracheal samples will be collected on Days 1 (prior to plasma administration), 3, 5, 8, 11, and 15.

Objectives: **Primary Objectives**

The overall objective of the study is to evaluate the safety and explore the efficacy of treatment with convalescent plasma plus standard care vs. standard care alone in hospitalized participants with confirmed COVID-19 disease.

Secondary Objectives

For the secondary objectives, we will compare treatment and control arms with clinical severity scales.

Primary Endpoint: The primary safety objective will be assessed by the cumulative incidence of serious adverse events (SAEs) at Study Day 29.

The primary efficacy objective will be assessed by comparison of clinical severity between participants in the treatment versus control arms, as measured by a modified 8-point ordinal severity score on Study Day 29. The modified score treats all participants who have reached levels 1-3 as recovered.

**Secondary
Endpoints:**

	SECONDARY OBJECTIVES	ENDPOINTS (OUTCOME MEASURES)
	
1. Evaluate the clinical efficacy of convalescent plasma administration by comparing treatment vs. control arms.
 
 • Clinical Severity 
 ○ Ordinal scale: 
 ■ Time to recovery, defined by time to levels 1-3 on the ordinal scale ■ Time to an improvement of one category and two categories from Day 1 using an ordinal scale. ■ Participant clinical status using ordinal scale at Days 3, 5, 8, 11, 15, 22, and 29. ■ Mean change in the ordinal scale from Day 1 to Days 3, 5, 8, 11, 15, 22, and 29. 	
• Clinical outcome assessed using ordinal scale daily while hospitalized and on Day 15, 22, and 29.
 
• Clinical status assessment (8-point ordinal scale) includes:
 
 1. Not hospitalized, no limitations on activities. 2. Not hospitalized, limitation on activities and/or requiring home oxygen; 3. Hospitalized, not requiring supplemental oxygen - no longer requires ongoing medical care; 4. Hospitalized, not requiring supplemental oxygen - requiring ongoing medical care (COVID-19 related or otherwise); 5. Hospitalized, requiring supplemental oxygen; 6. Hospitalized, on non-invasive ventilation or high flow oxygen devices; 7. Hospitalized, on invasive mechanical ventilation or ECMO. 8. Death

- National Early Warning Score (NEWS):
 - Time to discharge or to a NEWS of ≤ 2 and maintained for 24 hours, whichever occurs first
 - Change from Day 1 to Days 3, 5, 8, 11, 15, and 29 in NEWS
- Oxygenation:
 - Oxygenation free days to Day 29.
 - Incidence and duration of new oxygen use during the study.
- Non-invasive ventilation/high flow oxygen:
 - Non-invasive ventilation/high flow oxygen - free days to Day 29.
 - Incidence and duration of new non-invasive ventilation or high flow oxygen use during the study.
- Invasive Mechanical Ventilation / extracorporeal membrane oxygenation (ECMO):
 - Ventilator / ECMO free days to Day 29.
 - Incidence and duration of new mechanical ventilation or ECMO use during the study.
- **Hospitalization**
 - Duration of hospitalization.
- **Mortality**
 - Survival time
 - 14-day mortality
 - 28-day mortality

2. Evaluate the safety of convalescent plasma administration comparing treatment vs. control arms by:

- Cumulative incidence of Grade 3 and 4 clinical and/or laboratory AEs through Day 29.
- Changes in WBC with differential, hemoglobin, platelets, creatinine, glucose, total bilirubin, ALT, AST, and PT over time (analysis of lab values in addition to AEs noted above).
- SAEs
- Grade 3 and 4 AEs
- WBC with differential, hemoglobin, platelets, creatinine, glucose, total bilirubin, ALT, AST, and PT on Day 1; Days 3, 5, 8, and 11 (while hospitalized); and Days 15 and 29 (if lab collection is possible).

EXPLORATORY OBJECTIVES	ENDPOINTS (OUTCOME MEASURES)

Evaluate the clinical efficacy of convalescent plasma administration as compared to active drug (e.g., Remdesivir) recipients in DMID
 
Protocol Number: 20-0006 or other relevant COVID-19 Protocols
 
 • Clinical Severity 
 ○ Ordinal scale: 
 ▪ Time to recovery, defined by time to levels 1-3 on the ordinal scale ▪ Time to an improvement of one category and two categories from Day 1 using an ordinal scale. ▪ Participant clinical status using ordinal scale at Days 3, 5, 8, 11, 15, 22, and 29. ▪ Mean change in the ordinal scale from Day 1 to Days 3, 5, 8, 11, 15, 22, and 29. ○ National Early Warning Score (NEWS): 
 ▪ Time to discharge or to a NEWS of ≤ 2 and maintained for 24 hours, whichever occurs first ▪ Change from Day 1 to Days 3, 5, 8, 11, 15, and 29 in NEWS. ○ Oxygenation: 
 ▪ Oxygenation free days to Day 29. ▪ Incidence and duration of new oxygen use during the study. ○ Non-invasive ventilation/high flow oxygen: 
 ▪ Non-invasive ventilation/high flow oxygen - free days to Day 29. ▪ Incidence and duration of new non- invasive ventilation or high flow oxygen use during the study. 	
 • Clinical outcome assessed using ordinal scale daily while hospitalized and on Day 15, 22, and 29. • NEWS assessed daily while hospitalized and on Days 15 and 29 • Days of supplemental oxygen (if applicable) • Days of non-invasive ventilation (if applicable). • Days of high flow oxygen (if applicable).

- Invasive Mechanical Ventilation / extracorporeal membrane oxygenation (ECMO):
 - Ventilator / ECMO free days to Day 29.
 - Incidence and duration of new mechanical ventilation or ECMO use during the study.
- Days of invasive mechanical ventilation (if applicable).
 - Days of ECMO (if applicable).

Evaluate the virologic efficacy of convalescent plasma as assessed by:

- Percent of participants with detectable SARS-CoV-2 in OP or ET samples at Days 3, 5, 8, 11, and 15.
- Quantitative SARS-CoV-2 in OP or ET samples at Days 3, 5, 8, 11, and 15.
- Qualitative SARS-CoV-2 in OP or ET samples at Days 3, 5, 8, 11, and 15.

Evaluate the timing and titer of anti-SARS-CoV-2 antibody responses after convalescent plasma administration

- Plasma antibody binding and neutralization on Day 1; Days 3, 8, 15, 29, and 60

Evaluate the timing and quality of SARS-CoV-2 cellular responses after convalescent plasma administration

- Cellular responses in whole blood on Day 1; Days 3, 8, Days 15, 29, and 60

Evaluate the change in inflammatory responses with convalescent plasma administration

- Plasma and cellular markers of inflammation on Day 1; Days 3, 8, 15, 29, and 60

Evaluate the change in clinical status (by clinical severity score) to the change in inflammatory markers

- Ferritin, C Reactive Protein, D-Dimer, Fibrinogen, Erythrocyte Sedimentation Rate, Triglycerides, IL-6 on Study Day 1, 3, 5, 8, 11, 15, 29, and 60 (when available).

Study Population: Severely-ill, hospitalized adults ≥ 18 years old with COVID-19 pneumonia

Phase: Phase I

Enrolling Sites: This is a single site study conducted in the Hospitals of the University of Pennsylvania.

Description of Study Intervention: This open label, randomized, controlled, phase I study will assess the administration of 2 units of convalescent plasma collected from ABO-compatible donors who have recovered from COVID-19. Participants will be randomized 1:1 to receive either convalescent plasma on Study Day 1 in addition to standard care or standard care alone.

Study Duration: We expect the study to last 6 months from initiation

Participant Duration: An individual participant will complete the study in about 60 days, from screening at Day -1 or 1 to follow-up on Day 60 ± 5 days

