3.2 Secondary Objectives and Endpoints

For the secondary objectives, we will compare treatment and control arms based on the following list of clinical endpoints which capture different aspects of disease severity.

OBJECTIVES	ENDPOINTS (OUTCOME MEASURES)

1. Evaluate the clinical efficacy of convalescent plasma administration by comparing treatment vs control arms
 
 • Clinical Severity 
 ○ Ordinal scale: 
 ■ Time to recovery, defined by time to levels 1-3 on the ordinal scale ■ Time to an improvement of one category and two categories from Day 1 using an ordinal scale. ■ Participant clinical status using ordinal scale at Days 3, 5, 8, 11, 15, 22, and 29. ■ Mean change in the ordinal scale from Day 1 to Days 3, 5, 8, 11, 15, 22, and 29. 	
 • Clinical outcome assessed using ordinal scale daily while hospitalized and on Day 15, 22, and 29. • Clinical status assessment (8-point ordinal scale) includes: 
 1. Not hospitalized, no limitations on activities. 2. Not hospitalized, limitation on activities and/or requiring home oxygen; 3. Hospitalized, not requiring supplemental oxygen - no longer requires ongoing medical care; 4. Hospitalized, not requiring supplemental oxygen - requiring ongoing medical care (COVID-19 related or otherwise); 5. Hospitalized, requiring supplemental oxygen; 6. Hospitalized, on non-invasive ventilation or high flow oxygen devices; 7. Hospitalized, on invasive mechanical ventilation or ECMO; 8. Death

 ○ National Early Warning Score (NEWS): 
 ■ Time to discharge or to a NEWS of ≤ 2 and maintained for 24 hours, whichever occurs first ■ Change from Day 1 to Days 3, 5, 8, 11, 15, and 29 in NEWS. 	
 • NEWS assessed daily while hospitalized and on Days 15 and 29.

 ○ Oxygenation: 
 ■ Oxygenation free days to Day 29. ■ Incidence and duration of new oxygen use during the study. 	
 ■ Days of supplemental oxygen (if applicable)

OBJECTIVES	ENDPOINTS (OUTCOME MEASURES)

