8.1.2 Measures of clinical support, limitations and infection control

On each study day while hospitalized through Study Day 29, the following measures for the previous day will be recorded. i.e., on Day 3, Day 2 measures are assessed as occurring anytime in that 24 hour period (00:00 to 23:59h):

- Hospitalization
- Oxygen requirement
- Non-invasive mechanical ventilation (via mask) requirement

- High flow oxygen requirement.
- Invasive mechanical ventilation (via endotracheal tube or tracheostomy tube) requirement.
- ECMO requirement.
- Ongoing medical care preventing hospital discharge (COVID-19 related or other medical conditions)
- Limitations of physical activity (self-assessed).
- Isolated for infection control purpose

If drawn for clinical care, record inflammatory markers, including:

- Ferritin, C Reactive Protein, D-Dimer, Fibrinogen, Erythrocyte Sedimentation Rate, Triglycerides, IL-6.

If and when a participant is discharged from the hospital, they will continue with study visits as an outpatient, for all Study Days that are applicable, including Days 15, 29, and 60. Outpatient visits will involve the participant returning to clinic, unless other reasonable accommodations for evaluations and blood draws can be arranged. Day 22 Study visit can be as a phone call. Given the COVID-19 restrictions and the difficulty some of the participants might have to attend an in person visit after hospital discharge, the collection of Day 60 data for primary and secondary endpoints and the collection of Day 60 samples for exploratory tests may be performed up to 90 days following the Day 60 visit. For these participants, the Day 60 data may be obtained from the information already entered in the clinical records by any clinician, or by contacting the participant by phone up to 90 days following the Day 60 visit to obtain retrospective data.

8.1.3 *Ordinal Scale*

The ordinal scale is an assessment of the clinical status at the first assessment of a given study day. From the measures collected in 8.1.2.1, this ordinal scale can be constructed.

The scale used in this study is as follows:

1. Not hospitalized, no limitations on activities.
2. Not hospitalized, limitation on activities and/or requiring home oxygen;
3. Hospitalized, not requiring supplemental oxygen - no longer requires ongoing medical care;
4. Hospitalized, not requiring supplemental oxygen - requiring ongoing medical care (COVID-19 related or otherwise);

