9.2 Sample Size Determination

A total of 80 participants are expected to enroll and be randomized in a 1:1 fashion to one of two study arms. Sample sizes are determined by desire to estimate safety and to provide a preliminary idea of efficacy. Given patients will be hospitalized at enrollment, we expect very low missing data rates for early safety and efficacy endpoints. We also expect to be able to have good follow-up post discharge until the end of the study. Patients will be analyzed for safety if they receive at least one dose of the experimental treatment. For efficacy endpoints, analyses will be according to the intent-to-treat principle and outcomes on all enrolled participants will be included for analysis. All power calculations assume Type I error rate of alpha=0.05. Power calculations were done using STATA/SE v16.0.

With a sample size of 40 for a given arm, the expected probability of observing zero or at least one adverse event at varying underlying adverse event rates under a binomial distribution is shown below in Table 3. At this sample size, it is likely to see at least one person with an adverse event even with relatively small rates of adverse reactions. For example, 40 individuals in one arm, there is an 80% chance of observing at least one individual with an event if the underlying AE rate is 4%. The analysis of AE rates will primarily be descriptive due to the lack of power to make formal comparisons with the control arm.

Table 3. Probability of detecting zero individuals or at least one individual with an Adverse Event (AE) for a variety of different underlying AE rates and sample size N =40

AE rate	Pr(0 events)	Pr(1+ event)
0.001	0.96	0.04
0.005	0.82	0.18
0.01	0.67	0.33
0.02	0.45	0.55
0.03	0.30	0.70
0.04	0.20	0.80
0.05	0.13	0.87
0.10	0.01	0.99

While the sample size is driven by safety considerations, we also consider the operating characteristics of the proposed sample size for the analysis of the primary and secondary efficacy endpoints. The primary efficacy outcome is a comparison of the clinical severity score. The severity score is based on

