9.4 Statistical Analyses

9.4.1 General Approach

Descriptive statistics (mean, standard deviation, minimum, median interquartile range, and maximum values for continuous variables; and frequencies and percentages for categorical variables) will be computed for all study variables for the above populations. Unless otherwise specified, a complete case analysis will be considered such that missing values will not be replaced, and calculations will be done on available reported values. If there is a substantial amount of missing data we may consider imputation methods and adjust the analyses accordingly. Analyses will primarily be descriptive; estimates will be presented with 95% confidence intervals. Any significance testing will be done at the 0.05 level. Details for the primary and key secondary analyses are provided below. A formal Statistical Analysis Plan (SAP) will be developed prior to performing analyses of the study endpoints.

9.4.2 *Analysis of the Primary Endpoint(s)*

The primary safety endpoint is cumulative incidence of serious adverse events (SAEs) at Day 29, calculated separately by arm as the percent of individuals who had at least one SAE by Day 29. The SAE rate at all other time points of the study will also be calculated. The overall SAE incidence will be presented, as well as separately by system organ class and preferred term groupings. Percentages will be based on the number of participants who were treated (the safety analysis set). Additional frequencies will be presented with respect to maximum severity and to relationship to COVID19 and study product. Multiple occurrences of the same AE will be counted only once according to the highest occurring grade and relationship to study product/COVID19.

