Cumulative incidence curves will be considered for time-to-event endpoints, treating death as a competing risk. Gray's test, or if the cause-specific hazard ratio was of interest the log-rank test, will be used to compare groups. Binary proportions will be estimated along with Clopper-Pearson 95% confidence intervals and compared between arms using Fisher's exact test. Continuous endpoints will be summarized with means, SD and normal 95% confidence intervals; Wilcoxon rank-sum will be used to compare arms for continuous endpoints. Ordinal endpoints (e.g. 8-point clinical severity score) will be summarized by their multinomial proportions across the different categories at Study Day 15,

22 and 29. An exact Mann-Whitney test will be used to test for whether the ordinal clinical severity was higher in one arm versus the other for ordinal endpoints. Further details for the analysis of secondary endpoints will be provided in the Statistical Analysis Plan.

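### The duration-of-new-support endpoints have no stated denominator; read naturally, they compare arms only among participants who start support after randomisation, which can make the better arm look worse

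*Combined protocol and SAP*

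**What the plan says.** - **Purpose.** Section 3.2 places these endpoints under the objective "Evaluate the clinical efficacy of convalescent plasma administration by comparing treatment vs control arms", so they serve a between-arm efficacy comparison.
- **Endpoint.** Sections 1.1 and 3.2 list "Incidence and duration of new mechanical ventilation or ECMO use during the study", and repeat the form for oxygen and for non-invasive ventilation or high-flow oxygen.
- **Measure.** The matching outcome measure in 3.2 begins "Days of invasive mechanical ventilation (if applicable", a qualifier that assigns no value to someone never ventilated.
- **Missing values.** Section 9.4.1: "a complete case analysis will be considered such that missing values will not be replaced, and calculations will be done on available reported values".
- **Test.** Section 9.4.3: "Wilcoxon rank-sum will be used to compare arms for continuous endpoints". It assigns Fisher's exact test to proportions.
- **Analysis set.** Section 9.2 applies intent-to-treat to efficacy and adds that "outcomes on all enrolled participants will be included for analysis".
- **Data capture.** Section 8.1.2: "On each study day while hospitalized through Study Day 29, the following measures for the previous day will be recorded". Section 4.1 follows participants to Day 60.
- **Companion endpoints.** Support-free days to Day 29 are listed for each type of support. No rule for scoring deaths is given for them or for duration.

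**The concern.** Whether a participant starts new support is itself an outcome that plasma is meant to change. If duration is compared only among those who start, the two groups are no longer the randomised groups. When treatment keeps the milder cases off support, the treated users who remain are the more severe ones, with longer courses. An arm that spared participants from ventilation could then be reported as having longer ventilation. This happens even with no deaths; deaths during support shorten duration and add a second distortion.

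Excluding participants already on the support at Day 1 is not the problem, because that restriction is fixed before randomisation. The problem is the later restriction to users.

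There is also a mismatch of window: the endpoint runs over the whole study, to Day 60, but the daily record of support ends at Day 29.

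**Working it through.** **The plan's own figure.** The plan gives no figure for the duration endpoints. The nearest is in 9.2: about 80% power for event rates of 0.50 versus 0.80 with 40 per arm by chi-squared. With pooled rate 0.65 and two-sided alpha 0.05, z = [0.30 × √40 − 1.96 × √(2 × 0.65 × 0.35)] / √(0.25 + 0.16) = (1.897 − 1.322) / 0.640 = 0.90, so power is 81.6%. The figure reproduces, but it says nothing about duration.

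**Identity.** For participants at risk at Day 1, days per at-risk participant = incidence of new use × mean days among users. A users-only comparison looks at the second factor and ignores the first.

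**Worked example (assumed figures, no simulation).** Take 40 per arm, none ventilated at entry. Control has 8 courses of 5 days and 8 of 15 days. Plasma prevents 6 of the short courses and changes nothing else.

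| | Control | Plasma |
|---|---|---|
| Incidence | 16/40 = 40% | 10/40 = 25% |
| Mean days, users | (40 + 120)/16 = 10.0 | (10 + 120)/10 = 13.0 |
| Mean days, all at risk | 160/40 = 4.00 | 130/40 = 3.25 |

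If plasma prevents all 8 short courses, users-only means are 10.0 versus 15.0 days (Wilcoxon p = 0.018 against plasma), while the means over all at risk are 4.0 versus 3.0.

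**Simulation (assumed inputs; the documents give none).** There are 30 at risk per arm and no deaths. Severity S is standard normal, and the most severe 40% (control) or 20% (plasma) are ventilated. Duration = min(28, ceil(exp(1.9 + b·S + 0.6·e))), with e standard normal and b the dependence of duration on severity. Plasma has no other effect.

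- At b = 0.5, users-only means are about 13.1 and 15.3 days. By the identity, days per at-risk participant are 0.40 × 13.1 = 5.2 and 0.20 × 15.3 = 3.1.
- At b = 0.5, the users-only comparison points the wrong way in about 70% of trials, but significantly so in only about 7–8%.
- From b = 0 to b = 0.8, the plasma-to-control ratio of users-only means runs from about 1.0 to about 1.2. The users-only median is longer on plasma in 46% to 78% of trials. The 46% at b = 0 is chance with ties, not bias.

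**A second model** used 20 to 40 at risk per arm, control risk of 30% to 50%, and the mildest 25% to 50% of cases prevented. Users-only means are about 11.5 days on control and 13.2 to 15.3 on plasma, with plasma longer in 68% to 93% of trials. When prevention is unrelated to severity, the means are 11.5 and 11.5. Users number only about 6 to 20 on control and 3 to 15 on plasma.

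**The case against.** **The denominator is inferred.** A reader might conclude that the plan prescribes a biased users-only test. The documents do not go that far. The same qualifier is attached to the item on date and cause of death, where nobody would drop survivors from the mortality analysis. Section 8.1.2 records support on every hospital day, so a never-user has observed days without support and is not plainly missing. The intent-to-treat sentence in 9.2 could be read as scoring non-users 0. Section 9.4.3 also defers detail on secondary endpoints to the SAP, and the text available holds no separate SAP. This stands in part: the defect is an unstated denominator whose natural reading is the problematic one. The general intent-to-treat sentence does not give a duration to someone with no new use.

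**Lost power is not the right charge.** A reader might also infer that the endpoint throws away nearly all its power. In the simulation at b = 0.5, ranking all at-risk participants gives about 33%, but Fisher's exact test on incidence alone gives about 29%. Most of that power is the incidence effect, which the plan already tests. A users-only comparison answers a different question, and here plasma has no effect on an individual course once started.

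**An all-participant measure already exists.** Support-free days to Day 29 can be defined for everyone and overlap heavily with the proposed quantity. This stands, and is why relying on them for the test is an acceptable alternative.

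**The number at risk is unknown.** The 30 per arm has no basis in the documents. Section 4.1 describes a mechanically ventilated population, while 5.1 admits ordinal levels 5 to 7. With 10 to 15 at risk per arm, power over all at-risk participants falls to about 13–18%. This stands, and any test here will be weak.

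**Conclusion.** The concern holds as a gap in definition with a foreseeable bias. No denominator is stated for the three duration endpoints, and the natural reading compares groups formed after randomisation. Under the assumed 40% versus 20% incidence with 30 at risk per arm and milder cases prevented, this turns a fall from about 5.2 to 3.1 days per at-risk participant into an apparent rise from about 13 to 15 days among users. Reversal is possible, not inevitable: it depends on prevention falling on the milder cases.

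It would go too far to infer that the trial would declare harm or lose its efficacy evidence. A significant wrong-way result is uncommon even in the unfavourable model, a longer duration would be read beside a lower incidence, and 9.4.3 names survival and time to recovery as the key secondary endpoints. Analyses in this 80-participant phase 1 trial are primarily descriptive. It is a cheap correction worth making before outcome data are analysed.

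**What to change.** In 3.2 and 9.4.3, or in the SAP:

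1. Test incidence of new use as a proportion, as 9.4.3 already provides.
2. For duration, compare by rank test the days of that support from Day 1 to Day 29 in all randomised participants not on that support at Day 1, scoring 0 if never used. Alternatively, rely on the support-free-day endpoints for the between-arm test.
3. Write one explicit analysis rule for scoring deaths and apply it to both the days-of-support and the free-day endpoints; none is stated now.
4. Report duration among users descriptively, without a p-value.
5. End the window at Day 29, where daily capture stops, in place of the whole study.

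**Cost.** Wording only, using the in-hospital daily data already planned. Because that capture applies while hospitalised, the text should also say how home-oxygen days between discharge and Day 29 count. The tested quantity mixes need for support with its length and overlaps with free days. Given entry at levels 5 to 7, few participants may be at risk of new oxygen use, so the change matters most for ventilation and high-flow support.
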